7.2.5 Day n-1 (last day of treatment)

Day n-1 is the last day of treatment and corresponds to:

- Day of extubation due to improvement of patient condition. If a patient has to be re-intubated within 24 hours he will remain in the study and treatment with study drug continued daily until 2nd extubation successful or until Day 20 of treatment whatever happens first
- Exitus day
- Day 20: Treatment with study drug will be stopped even if ventilation will be continued

The required tests will correspond to Day 3 requirements with additional items for discharge unless not feasible:

- Adverse events from previous night
- Local tolerance
- Body temperature (tympanic or rectal) ~7:00
- Blood pressure, heart rate, respiration rate (~8:00)
- Blood gases
- Oxygenation: Pa_{O2}/ FI_{O2}
- Tracheal aspirate #1, collected pre last dose early morning if patient still ventilated for transfer to local laboratory for:
 - Quantification of *P. aeruginosa*
 - Isolation of *P. aeruginosa* strain and storage at -70°C
 - Special Day n-1 assessment for MIC on *P. aeruginosa* strain with 11 antipseudomonal antibiotics (listed under Section 6.2)
- ECG 1-4 hours post drug
- Lung X-ray whenever possible that day
- CPIS (use lung X-ray of same day)
- Clinical endpoints
- APACHE II score
- Tracheal aspirate #2 (for freezing at -70°C and transfer to Geneva laboratory for investigation), collected 6 hours post drug or earlier if extubation planned
- Extubate if applicable, if possible in the afternoon and after collection of tracheal aspirate sample 2, as medically indicated by weaning procedures
- Store ventilation device in sterile pouch at -70 °C, pending shipment to Geneva laboratory

In the case of exitus, the examinations performed on the previous day and on last third day (Day 9, 12, 15 etc.) will be used as Day n-1 values and the respiration device will be recovered and stored as described above.

On **Day n**, no study drug will be administered and the patient will be discharged from the study after physical examination and after collecting blood and urine safety samples. Ventilation will be continued if required.

7.2.6 Poststudy (Day n + 7)

Information on the patient outcome (pneumonia, infection, strain, etc.) and intercurrent adverse events over the past week will be collected one week after cessation of therapy, i.e. on Day n+7, even for patients treated with antipseudomonal antibiotherapy, whether ventilated or not. This information will be best achieved by the treating physician visiting the patient at his present location or by obtaining a report.

The Quintiles study monitor will control the labeling, storage, and coordinate the shipment of all biological samples collected during the study by the ICU nurse to the University Hospital of Geneva, Switzerland. Shipment will be performed in batches of patients when convenient for site, monitor, and Geneva laboratory (see Appendix G).

7.3. Methods of evaluation

Clinical efficacy (clinical site)

All clinical variables will be collected at the clinical site, within the ICU, by a designated subinvestigator and ICU nurse, whenever possible by the same individuals for a given patient, barring emergencies.

Pharmacodynamic data (local laboratory)

Selected pharmacodynamic data (tracheal aspirate 1: quantitative count for *Pseudomonas aeruginosa* on Day -1, 1, 3, 6, 9, 12, 15, 18 and last day (Day x, or Day n-1, or Day 20), MIC to *P.aeruginosa* for 11 standard antipseudomonal antibiotics on Day -1 and on last day (Day x, or Day n-1, or Day 20) (see list in Section 6.2), CFU for other strains if indicated; BAL: CFU/mL, cellularity) will be performed in local bacteriology laboratory on a daily basis. MIC will be performed by one standard assay (disk diffusion assays as defined by the NCLS (National Committee for Laboratory Standards, or E-test, or dilution). All parameters will be assessed under double blind conditions for treatment.

Pharmacodynamic data (Geneva laboratory)

Extensive pharmacodynamic data both *in vivo* (tracheal aspirates 2: content for autoinducers,; mRNA for lasB elastase (lasI, rhlI); BAL: CFU/mL, autoinducer content; Respiration device: CFU/cm², autoinducer content) and *in vitro* (isolated strains from tracheal aspirates prepared by local laboratory, BAL and respiration device: virulence factor production, autoinducer production, azithromycin gradient plates for detection of rhamnolipid production) will be performed in the laboratory of [name] [name], Department of Genetics and Microbiology, Medical School, University of Geneva, Switzerland).

This list is provided as an example only and final parameters finally agreed upon may differ and will be described in a separate document which will be produced before unblinding the study and will be attached to the final Clinical Study Report. Details on samples to be analyzed are provided in Section 7.2.3. The control patients will be selected by an independent physician who will be given access to the allocation code, pairing 2 control patients by site (1 treated with azithromycin, 1 treated with placebo) with a pneumonia patient, but not by sex or age if not achievable. All parameters will be assessed under double blind conditions for treatment allocation, but not for study day.

Laboratory safety

Hematology and clinical chemistry will be carried out according to standard operating procedures of each study site central laboratory. Predefined percentage values will be used for parameters outside normal range.

Abnormal results which do not appear to be linked to underlying pathology will be verified to rule out laboratory error. Persistent relevant abnormal values must be followed up until the cause is determined or until they return to the premedication value. Any abnormality detected at 24 hour post drug intake should be followed up until resolution or stabilization.

Clinical safety

Blood pressure and heart rate will be recorded in supine position, with sphygmomanometry or automated measurements (Dynamap or alike, central line), always using same arm, same technique, and same equipment.

Adverse events spontaneously reported or observed by the investigator will be recorded. All adverse events, including intercurrent illnesses, must be reported and documented on the CRF.

Local tolerance at test drug site will be assessed at regular intervals during each infusion (0, 1, 2, 4, 8, 24 hour or longer in case of local reaction) but only if a peripheral site is used. Any symptoms rated as moderate or severe will be reported as an adverse event. An overall grading will be used with the following scale:

- | | |
|---|---|
| 0 | No irritation |
| 1 | Painful site, no erythema, no swelling, no induration, no palpable venous cord |
| 2 | Painful site with erythema and some degree of swelling, or both, but no induration and no palpable cord |
| 3 | Painful site with erythema and swelling, and with induration or a palpable cord ≤ 7 cm above site |
| 4 | Painful site with erythema, swelling, induration, and a palpable cord >7 cm above site |
| 5 | Frank vein thrombosis in addition to grade 4 signs and symptoms |

Rotating infusion sites every 4 or 5 days is encouraged to avoid problems with local tolerance. Site changes with vein involved and type of catheter (peripheral, central) will be recorded in the CRF. No local tolerance will be recorded if a central line is used. A central line will be used if available.

Twelve-lead ECG will be recorded as described in Appendix I, at a speed of 25 mm/sec and calibrated at 10 mm/mV. If a QTc is prolonged (>450 ms or >60 ms vs. baseline), manual checking of QT and calculation of QTc with Bazett's formula will be performed by the investigator for safety purposes. Manual reading will be performed at study completion by experienced cardiologist on study site. To perform centralized reading is not planned unless required at later stage.

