ED ₅₀	Effective dose at 50% of maximum pharmacological effect
ELF	Epithelial lining fluid
ERC	Ethical Review Committee
FI _{O2}	Percentage of inspired oxygen
Gamma-GT	Gamma glutamyltransferase (γ-GT)

Clinical Study Protocol ANB 006 #2001

GCP	Good Clinical Practice
GFR	Glomerular Filtration Rate
GI	Gastrointestinal
Hct	Hematocrit
HIV	Human Immunodeficiency Virus
HPLC	High Pressure Liquid Chromatography
HR	Heart Rate
i.v.	Intravenous
IC ₅₀	Inhibitory concentration eliciting 50% of maximum effect
ICH	International Committee for Harmonization
ICU	Intense Care Unit
MAC	Mycobacterium avium complex
MBP	Mean blood pressure (1/3 SBP + 2/3 DBP)
MCH	Mean corpuscular hemoglobin
MCHC	Mean corpuscular hemoglobin concentration
MCV	Mean corpuscular volume
MIC	Minimum inhibitory concentration
N	Number of observations
Pa _{O2}	Partial pressure of arterial oxygen
Pa _{O2} /FI _{O2}	Oxygenation
PBS	Protected brush specimen
PC	Predefined change
PD	Pharmacodynamics
PEEP	Positive end-expiratory pressure
PK	Pharmacokinetics
PT	Prothrombin time
QT	Duration between Q wave and T wave on the ECG (expressed in ms)
QTc	Corrected QT-interval (Bazett's formula) in ECG
RBC	Red blood cells
SAE	Serious adverse event
SBP	Systolic Blood Pressure
SD	Standard deviation
t _½	Elimination half-life in plasma
t _{max}	Time to reach maximal drug concentration in plasma
V	Volume of distribution
VAP	Ventilator associated pneumonia
WBC	White blood cells

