2. STUDY OBJECTIVES

Primary objective

- To assess the clinical efficacy of azithromycin 300 mg i.v., used as a quorum-sensing blocker, when compared to placebo for preventing or delaying the occurrence of pneumonia in ventilated patients colonized with *Pseudomonas aeruginosa*

Secondary objectives

- To assess other clinical efficacy variables
- To compare safety profile in target population
- To demonstrate using both *in vivo* and *in vitro* parameters whether azithromycin can be used clinically as a quorum-sensing blocker against *P. aeruginosa*
- To determine whether *P. aeruginosa* can develop resistance to the quorum-sensing blocker effect of azithromycin
- To check whether prolonged treatment with azithromycin may induce resistance to any of 11 antipseudomonal antibiotics
- To verify whether emergence of resistance to other bacteriae may be elicited by assessing rate of infections in both study groups (azithromycin vs. placebo)

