6.2 Prior and Concomitant Treatments - Antibiotherapy

Any treatment that are given in addition to the study treatment during the study is regarded as a concomitant treatment and must be documented on the appropriate pages of the CRF and in the subject's medical records, with dose adjustments as and if required. It is expected that a broad spectrum of concomitant treatments will need to be administered to treat the basic underlying disease or condition of these patients, to alleviate their symptoms, or to anticipate possible complications.

This may include antibiotics to treat infections, whenever possible selecting however an agent deprived of activity against *P. aeruginosa* or having demonstrated lack of activity against the specific strain isolated in that given patient. It is recommended to select an antibiotic to be used prior to or during the study for intercurrent infections from the table provided below to facilitate the choice of the investigators, to homogenize antibiotic treatment according to type of infections, and to limit interference with *P. aeruginosa* activity; one of these antibiotics should be given preferentially for empiric as well as for definitive therapy unless the clinical indication and/or resistance profile would justify another antibiotherapy.

Type of Infection	Recommended Antibiotics Deprived of Antipseumonal Activity
Vascular line infections	Methicillin, flucloxacillin, vancomycin, teicoplanin, synergid
Abdominal infections	Ceftriaxone +/- metronidazol
Urogenital infections	Ceftriaxone +/- metronidazol Amoxicillin + clavulanic acid +/- metronidazol
Pulmonary infections	Cetriaxone Amoxicillin + clavulanic acid
Central nervous system infections	Ceftriaxone, vancomycin
Skin infections	Penicillin, vancomycin, teicoplanin Amoxicillin + clavulanic acid

The following antibiotics listed in the table below have antipseudomonal activity and should be avoided for therapy unless the specific colonizing strain happens to be resistant or if mandatory during the study for clinical reasons. These same 11 antibiotics will be screened for MIC on bronchotracheal aspirate at study completion for assessing emergence of resistance.

11 Standard Antipseudomonal Antibiotics Not Recommended for Clinical Use* To Be Tested for MIC Pattern	
Carbenicillin	Ceftazidime
Piperacillin	Gentamycin
Piperacillin + tazobactam	Tobramycin
Imipenem	Amikacin
Ciprofloxacin	Meropenem
Cefepime	

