7.1.2. Pharmacodynamic data performed in local laboratory

A. Tracheal aspirates (on Aspirate 1)

- Collection daily
- Quantitative culture for *P. aeruginosa* (CFU/mL) on Day -1, 1, 3, 6, 9, 12, 15, 18 and last day (Day x, or Day n-1, or Day 20)
- Isolate *P. aeruginosa* strain daily and store at -70°C on skim milk and glycerol
- Emergence of resistance (MIC to *P. aeruginosa* in tracheal aspirate for 11 standard antipseudomonal antibiotics on Day -1 and on last day (Day x, or Day n-1, or Day 20) see list under Section 6.2)
- CFU for other strains from tracheal aspirates if indicated

B. BAL on Day x (or protected brush specimen (PBS) or bronchotracheal aspirate)

- Only for patients with suspected pneumonia for diagnosis
- CFU/mL
- Cellularity

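### Section 7.3 accepts disk diffusion as an MIC assay, so sites that use it cannot supply the numeric MIC change by which the protocol measures emergence of resistance

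*Protocol*

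**What the plan says.** Section 2 lists among the secondary objectives: "To check whether prolonged treatment with azithromycin may induce resistance to any of 11 antipseudomonal antibiotics". Section 7.1.2 turns this into a variable: "Emergence of resistance (MIC to *P. aeruginosa* in tracheal aspirate for 11 standard antipseudomonal antibiotics on Day -1 and on last day". The Synopsis says the same, the visit descriptions in Sections 7.2.2 and 7.2.5 schedule the test, and the abbreviation list expands MIC as "Minimum inhibitory concentration".

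Section 7.3 says how the measurement is made. The work "will be performed in local bacteriology laboratory on a daily basis", and the rule on method reads "MIC will be performed by one standard assay (disk diffusion assays as defined by the NCLS", followed by E-test or dilution as the other permitted methods. No method is chosen among the three, and no conversion between them is given.

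Section 5.3 targets 20 sites and allows up to 25. Section 11.3 lets pharmacodynamic variables be analysed as yes/no events, raw values, log-transformed values, differences from baseline or percentage changes.

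**The concern.** The variable is named and defined as a concentration, but one of the three permitted methods does not produce one. A laboratory can follow Section 7.3 to the letter and have nothing to enter as an MIC at either visit.

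The choice is made at the bench when the isolate is tested. A later analysis plan can choose how to analyse what was recorded, but it cannot recover a concentration from a zone diameter or a category.

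At stake is how sensitive the trial is to induced resistance. If the only scale common to all sites is the susceptibility category, a strain whose MIC rises without crossing a breakpoint counts as unchanged. The result then leans towards reporting no emergence of resistance.

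**Working it through.** The protocol gives no figure to reproduce. The check is on measurement scale, with a short count for scope.

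**1. What each permitted method yields**

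| Method | Direct reading | Numeric MIC | Susceptibility category |
|---|---|---|---|
| Dilution | Concentration | Yes | Yes, by breakpoint |
| E-test | Concentration | Yes | Yes, by breakpoint |
| Disk diffusion | Zone diameter | No | Yes, by zone breakpoint |

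**2. What the variable needs.** Sections 7.1.2 and 7.3 ask for an MIC on Day -1 and on the last day. The within-patient change is last-day MIC minus Day -1 MIC, or the same on a log scale. Both terms are missing at a disk site, so the change is missing too, and there is nothing to pool with E-test or dilution results.

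**3. What can still be derived.** Section 11.3 permits a yes/no form. Susceptible on Day -1 and resistant on the last day, per antibiotic, can be read from all three methods using each method's own breakpoints. It can be combined across sites, with some misclassification between methods.

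**4. What the yes/no form misses.** Let the breakpoint for resistance be B.
- If the MIC rises from m to 4m and 4m is still below B, the category change is zero although the MIC rose fourfold.
- If the Day -1 MIC is already at or above B, a susceptible-to-resistant change cannot occur. Sections 4.3 and 6.2 deliberately create such cases: a patient already on an antipseudomonal antibiotic is admitted when the colonizing strain is resistant to it. For that drug and strain, a category change cannot show further worsening.

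**5. Whether another planned assay fills the gap.** The Geneva programme in Sections 7.1.3 and 7.3 covers autoinducers, virulence factors and azithromycin gradient plates. It does not list MICs for the 11 antibiotics. Section 7.3 does call that list an example that may change before unblinding, so a test could be added, but none is planned.

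**6. Scope**
- Per patient: 2 isolates × 11 antibiotics = 22 determinations, giving 11 paired changes.
- For 100 assessable patients: 100 × 22 = 2,200. For 200: 200 × 22 = 4,400.
- These are maxima. Section 7.2.5 collects the last-day aspirate 1 only if the patient is still ventilated.
- If a share f of patients is at disk sites, f × 2,200 to f × 4,400 determinations carry no MIC. The documents do not give f. At f = 0 the count is 0; at f = 1 it is the full 2,200 to 4,400.

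**The case against.** The strongest reply is that the objective concerns resistance, not concentration. A susceptible-to-resistant change answers it, all three methods give that change, and Section 11.3 allows it. This stands. A reader might infer that emergence of resistance cannot be assessed at disk sites or cannot be combined across sites. The documents support that only for the numeric MIC.

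Zone diameter is itself quantitative, and Section 11.3 allows raw values and differences. A fall in zone size within a patient can show a shift inside one category. This also stands in part: it is usable information, but it is not an MIC, it is not on the scale of the other two methods, and the protocol does not say that the diameter is recorded.

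A reader might also infer that the information is gone for good. It is not: Section 7.1.2 and Appendix D have strains stored at -70 °C and shipped to Geneva, so retesting is possible, though unplanned.

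The reference to one standard assay may mean one method per laboratory or for the whole study. The list of alternatives and the use of local laboratories make a choice by site more likely. The phrase does suggest one method at both visits within a laboratory, but does not clearly require it. If one study-wide method was meant, none has been named, and disk diffusion is still on the list.

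Randomization in blocks of 4 within each site (Section 5.3) gives both arms much the same mix of methods. Differences between sites should therefore not bias the comparison of arms. The loss is in sensitivity and precision.

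Finally, Section 6.2 says "These same 11 antibiotics will be screened for MIC on bronchotracheal aspirate at study completion for assessing emergence of resistance", from which a reader might infer that the baseline test was left out. That sentence is not exclusive. Sections 7.1.2 and 7.3 give Day -1 and last day, and Section 7.2.2 lists the test among the Day -1 procedures.

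**Conclusion.** Section 7.3 is wrong as written: it lists as an MIC method one that does not yield the concentration the protocol defines and calls for. At sites using disks, the numeric MIC and its change from Day -1 to the last day are unavailable and cannot be pooled with E-test or dilution values. The susceptibility-category change remains available at every site, but it is blind to MIC rises within a category and to worsening in strains already resistant at entry.

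The effect is confined to one secondary objective. The primary endpoint, the sample size and the rule for stopping recruitment are untouched. Its size depends on the share of sites using disks, which the documents do not give and which can lie anywhere from none to all.

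The conclusion rests on what the three methods measure, and on reading the list in Section 7.3 as a choice left to the sites. The point is worth correcting before the first isolate is tested, because the choice of assay cannot be undone in the analysis.

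**What to change.** Amend Section 7.3 in one of two ways.

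1. **Keep the variable as an MIC.** Remove disk diffusion from the methods permitted for it, require E-test or dilution, and require the same method for a patient's Day -1 and last-day isolates. Stored strains allow the pair to be tested together.
2. **Redefine the variable.** Call it change in susceptibility category between Day -1 and the last day, judged by each method's own breakpoints. Report disk-diffusion sites on that scale only, apart from any numeric MIC, and state that rises within a category are not captured.

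The first option keeps the more sensitive measure. It costs a wording change plus consumables at sites that would have used disks. The second costs wording only and accepts the lower sensitivity. Neither needs new patients or new samples.

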7.1.3 Pharmacodynamic data performed in Geneva laboratory

A. Tracheal aspirates (*ex vivo*, on Aspirate 2)

- Collection daily at study site, storage at -70°C prior to transfer to Geneva
 - Day -1, 1, 3, 6, 9, ..., last day (Day x, or Day n-1, or Day 20) for all patients
 - Daily for pneumonia (n=10) and control patients (n=20)
 - Daily for patients on antibiotherapy
- Parameters
 - Content for autoinducer homoserine lactones: 3-oxo-C₁₂-HSL and C₄-HSL **and/or**
 - mRNA for LasB elastase (lasI, rhlI)

B. Respiration device on Day n

- CFU/cm²
- Autoinducer content

C. Isolated *P.aeruginosa* strains from tracheal aspirate 1 and respiration device (*in vitro*)

- Day -1, 1, 3, 6, 9, ..., last day (Day x, or Day n-1, or Day 20) for all patients Daily for pneumonia (n=10) and control patients (n=20) selected on a site basis
- Daily for patients on antibiotherapy
- *In vitro* virulence factor production (elastase, protease, rhamnolipids, cytotoxicity)
- *In vitro* autoinducer production (3-oxo-C₁₂-HSL and C₄-HSL)
- Azithromycin gradient plates for detection of rhamnolipid production (Day -1, or Day x, or Day n-1) to detect possible resistance mechanisms

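### In the daily case-control subset, a physician who knows the allocation code chooses the 20 controls with no selection rule, so comparing arms among them is open to selection bias

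*Protocol*

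**What the plan says.** Section 7.1.3 sets three sampling schemes for the Geneva assays on tracheal aspirates and isolated strains:

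- all patients: "Day -1, 1, 3, 6, 9, ..., last day (Day x, or Day n-1, or Day 20) for all patients";
- a case-control subset: "Daily for pneumonia (n=10) and control patients (n=20";
- a further group: "Daily for patients on antibiotherapy".

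Section 7.3 explains how the controls are found: "The control patients will be selected by an independent physician who will be given access to the allocation code". The structure is "pairing 2 control patients by site (1 treated with azithromycin, 1 treated with placebo) with a pneumonia patient", with the qualification "but not by sex or age if not achievable". It adds: "All parameters will be assessed under double blind conditions for treatment allocation, but not for study day".

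The assays serve a secondary objective in section 2, which asks "whether azithromycin can be used clinically as a quorum-sensing blocker against" *P. aeruginosa*.

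**The concern.** To obtain one control per arm, somebody must know the code. The weakness is that the person who knows it also has discretion over whom to take. Section 7.3 gives no random draw, order-of-entry rule, eligibility definition or tie-break. It does not say whether a control must be free of pneumonia or still ventilated on the study day when the case was diagnosed, and it does not limit what the physician may see.

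Timing makes this more than formal. Under Appendix D the second daily aspirate is frozen, and samples not assayed can be kept in reserve. Controls can therefore be chosen after a patient's course is known. A selector who knows the arm could, without intending it, take quieter courses on azithromycin or worse ones on placebo. Laboratory blinding protects the measurement but comes too late to protect the selection.

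The controls carry most weight if the drug works well. In the full-protection scenario of section 11.5 all 10 cases are on placebo, so the 10 selected controls would be the only azithromycin patients in the 30-patient case-control subset.

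**Working it through.** **Inputs from the Protocol.** 10 cases and 20 controls (7.1.3); two controls per case, one per arm, same site (7.3); 100 to 200 assessable patients (4.1); 20 sites targeted, 25 at most (5.3); two arms.

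**Assumptions, not in the Protocol.** The selector sees a clinical marker that correlates with the assay value at rho = 0.3 (range shown: 0.2 to 0.5). Values are normal. There is no true treatment effect.

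**1. The Protocol's own count.** 10 cases x 2 controls = 20, that is 10 per arm. This agrees with section 7.1.3.

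**2. Share of the trial.** The subset is 10 + 20 = 30 patients: 30/200 = 15% to 30/100 = 30% of assessable patients.

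**3. Is there room for choice?** Average assessable patients per site and arm:

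- 100 / 25 / 2 = 2
- 100 / 20 / 2 = 2.5
- 200 / 25 / 2 = 4
- 200 / 20 / 2 = 5

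The average is 2 to 5 before cases are removed, so there will often be more than one candidate, although matching on sex and age narrows the field. At the low end, the case uses one of the two places in its own arm. One candidate then remains there, and only the other arm offers a choice.

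**4. Worst-case bias.** If the selector takes the lowest of m candidates on the marker in one arm and the highest of m in the other, the spurious difference is 2 x rho x E(maximum of m standard normals).

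- m = 2: 2 x 0.3 x 0.56 = 0.34 SD
- m = 4: 2 x 0.3 x 1.03 = 0.62 SD

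**5. Simulation.** 20,000 runs of 10 same-site control pairs, compared by a paired t-test at two-sided 0.05, with rho = 0.3:

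| Candidates per arm | Both arms steered: bias (SD), type I error | One arm steered: bias (SD), type I error |
|---|---|---|
| 2 | 0.34, 0.105 | 0.17, 0.063 |
| 3 | 0.50, 0.18 | 0.26, 0.081 |
| 5 | 0.69, 0.30 | 0.35, 0.11 |

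With a random choice, or with the same rule in both arms, the bias is about 0 and the type I error 0.047 to 0.053.

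**6. Sensitivity.** Over rho 0.2 to 0.5 and m 2 to 5:

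- both arms steered: bias 0.23 to 1.16 SD, type I error 0.07 to 0.70;
- one arm steered: bias 0.12 to 0.58 SD, type I error 0.055 to 0.23.

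**7. Yardstick.** The standard error of a 10 vs 10 difference is sqrt(2/10) = 0.447 SD. At rho = 0.3 the worst-case bias is 0.34/0.447 = 0.76 to 0.69/0.447 = 1.5 standard errors.

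Assay blinding appears nowhere in these steps and cannot alter the result.

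**The case against.** **The mechanistic evidence does not rest on this subset.** A reader might infer that the whole azithromycin-placebo contrast on quorum sensing is compromised. The Protocol does not support that. The same Geneva assays run about every third day in all patients, which gives a contrast that the physician does not select. The daily set on antibiotherapy is not selected by the physician either. This stands, and it confines the point to the case-control subset.

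**No stated analysis compares 10 with 10.** The pairing is a case-control structure. Section 11.3 plans to analyse the variables in all patients and by antibiotic subgroup. Nothing names the 20 controls as the test of quorum-sensing blockade. This also stands: the concern applies to such a comparison if it is made.

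**Discretion is limited and misuse is not shown.** The physician is described as independent, and arm, site and, where achievable, sex and age are fixed. Nothing says that the physician sees the clinical course or the assay results, and the bias needs some such knowledge. A reader might infer that the selection will be steered, but the text shows only that it could be.

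**The rule may come later.** Section 11.3 promises a detailed statistical plan before decoding, and a draw rule could be placed there. That answers a complaint about missing detail. It does not fully answer this one, because the Protocol itself assigns the selection to a person who knows the code. The separate document announced in section 7.3 concerns the assay parameters.

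**Conclusion.** The point holds for the daily case-control subset only. Any azithromycin-placebo comparison among the 20 selected controls is open to selection bias that blinded assays cannot remove. The all-patient mechanistic data and the primary pneumonia endpoint are not affected.

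The bias is possible, not certain, and its size cannot be derived from the documents. The range of 0.34 to 0.69 SD is a worst case. It rests on an assumed correlation of 0.3, on 2 to 5 candidates per arm, and on steering in opposite directions at every site. If only one arm is steered, or only one arm offers a choice, it is about half. If one rule is applied alike in both arms, it is about 0, even when that rule is not random. Knowledge of the code is therefore harmful only in combination with discretion.

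This is a worthwhile, cheap improvement to a secondary, exploratory part of the trial and not a threat to its main conclusion.

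**What to change.** In section 7.3, replace selection by the physician with a documented draw:

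- **Eligible list.** Define it in advance, for example same-site patients who are pneumonia-free and still ventilated at the case's Day x. Have it compiled by someone blinded to arm.
- **Draw.** The independent statistician, who already prepares the randomization lists (section 5.3), draws one control per arm at random with a recorded seed. The statistician has no access to clinical course or assay data for this purpose.
- **Matching.** Keep the pairing by site, and by sex and age where achievable, as a restriction on the list before the draw.
- **Fallback.** State in writing what happens when a site has no eligible control in one arm.
- **Main contrast.** Name the all-patient samples as the main treatment comparison for quorum-sensing blockade, with the daily subset as supporting, descriptive evidence.

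The cost is a few sentences and a short program. Sample collection and assay numbers stay as planned, and no clinician needs the code for this purpose. The one real downside is the fallback, which loosens site matching in the cases where it is used.
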